6.1.2. Definitions and Conventions

The **baseline value** is the last value observed prior to the first dose of study drug

The **study day** will be calculated in reference to the first dose date of selpercatinib as follows:

- assessment date/event date – first dose date + 1, if assessment date or event date \geq first dose date,
- assessment date/event date – first dose date, if assessment date or event date < first dose date.

Unless otherwise noted, **summaries of continuous variables** will include a mean, median, standard deviation, minimum, and maximum.

Unless otherwise noted, **summaries of categorical variables** will include the frequency and percentage (relative to the population being analyzed) of each category.

Duration is calculated as:

- Duration (days): (End date – Start date + 1)
- Duration (weeks): (End date – Start date + 1) / 7
- Duration (months): (End date – Start date + 1) / 30.4375
- Duration (years): (End date – Start date + 1) / 365.25

6.2. Adjustments for Covariates

No adjustment for covariates is planned for this study.

6.3. Handling of Dropouts or Missing Data

Missing data will not be imputed with the exception of dates. The method of imputation for any dates is described in relevant section.

6.4. Multiple Comparisons/Multiplicity

No adjustment for multiplicity is planned for this study.

6.5. Patient Disposition

A detailed description of patient disposition will be provided. It will include a summary of the number and percentage of patients entered into the study, enrolled in the study, reasons for discontinuation from study treatment, and reasons for discontinuation from the study. Reason for discontinuation from both study treatment and the study will be listed by the pre-determined categories. If the reason for discontinuation is adverse event (AE) or death, the associated AE or cause of death will be reported. All patients entered in the study will be included in the summary.

The number and percentage of patients will be summarized by the enrolling study center. In the event a patient transferred to another center during the study, the center of original enrollment will be used for this tabulation.

Patients with progressive disease may be allowed to continue study drug if, in the opinion of the Investigator, the patient is deriving clinical benefit from continuing study treatment, and continuation of treatment is approved by the Sponsor. The number and percentage of such patients continuing to receive study drug after the documentation of disease progression will be presented.

6.6. Patient Characteristics

6.6.1. Demographics

The following variables will be summarized for all enrolled patients and PAS:

- Age
- Age group (<60, >=60)
- Sex (male, female)
- Height (cm)
- Weight (kg)
- Body mass index (BMI)
- ECOG performance status
- Smoking history (never smoked, current smoker, former smoker)

6.6.2. Baseline Disease Characteristics

The following disease characteristics will be summarized for all enrolled patients

- Stage of disease at enrollment (I–IV)
- Time since initial diagnosis (months)
- Metastatic disease at enrollment (yes, no)
- Time since initial diagnosis of metastatic disease (months)
- CNS metastasis by IRC assessment (yes, no)

Missing or partially missing dates for initial disease diagnosis will be imputed. If the month and year of the diagnosis are provided but the day is missing, the missing day is imputed as 15. If only the year is provided, then the missing month and day are imputed as July 1st for the calculation.

Stage of disease and disease metastasis will be derived from TNM staging. If M = M1, then the subject has metastatic disease, and vice versa.

Time since initial diagnosis will be calculated as (First dose date – Initial diagnosis date + 1) / 30.4375. Time since initial diagnosis of metastatic disease will be derived similarly.

6.6.3. Pre-existing Conditions and Historical Illnesses

Historical illnesses are clinically relevant events in the past that ended before the screening visit, while pre-existing conditions are events that are still ongoing during the screening visit. Both will be summarized for all enrolled patients and PAS by MedDRA PT.

6.6.4. Prior Therapies

The following variables will be summarized for all enrolled patients:

- prior systemic treatments (yes, no)
- prior radiotherapy (yes, no)
- prior cancer-related surgery (yes, no)
- type of prior systemic treatments (e.g., platinum-based chemotherapy, anti-PD-1/PD-L1 antibody, selective TKI inhibitors (EGFR, ALK, ROS1, etc), multikinase inhibitors (cabozantinib, vandetanib, etc), other prior systemic therapies)
- number of prior multikinase inhibitors used (0, 1, 2)
- number of prior systemic regimens (0, 1, 2, ≥ 3)
- number of prior systemic regimens (as a continuous variable)
- number of prior treatment lines (0, 1, 2, ≥ 3)
- best overall response to most recent prior systemic regimen (CR, PR, SD, PD, NE, unknown)

The number of prior treatment lines is defined as the number of distinct dates of progressive disease.

6.6.5. Post-Discontinuation Therapies (PDT)

Post-discontinuation anti-cancer therapies, including systemic therapies, radiotherapies and surgeries, will be summarized for all enrolled patients and PAS. Systemic therapies will also be summarized by medication class and specific medication terms. The number of patients who received 1, 2, 3... subsequent regimens will be summarized.

Patient-level listings of PDT will be provided.

6.6.6. *RET* Alteration

The following variables will be summarized for all enrolled patients and PAS to describe the distribution of known *RET* alterations at enrollment:

- *RET* alteration documented (fusion, mutation)
- *RET* fusion gene (KIF5B/CCDC6/NCOA4, other, unknown)
- *RET* testing sample (tissue, blood)
- *RET* testing lab for eligibility (local, central)
- Consistency between local and central testing results
- *RET* mutation type (M918T, extracellular cysteine mutation, other)
 - Extracellular cysteine mutation is defined as mutation including at least 1 of the following: C609*, C611*, C618*, C620*, C630# and C634*, where * is any letter in {F, G, R, S, W, Y}, and # is any letter in {R, Y}

The presence of *RET* fusion genes and *RET* mutations will be based on local testing performed prior to enrollment or during the screening phase of the study.

6.6.7. Tumor Burden

The following variables will be summarized for all enrolled patients and PAS to characterize the extent of disease at enrollment:

- Number of measurable lesions
- Sum of the diameters of target lesions (mm)

Findings from investigator assessments of baseline radiographic scans will be used to characterize the disease burden of patients at baseline. Assessments will be performed using RECIST 1.1. Additionally, findings from the IRC assessments of the baseline radiographic scans will be summarized in the same manner.

6.7. Treatment Compliance

Treatment compliance of selpercatinib will be measured by capsule counts and summarized over the whole treatment period for the safety population. Compliance will be calculated as the ratio of total dose taken to the total dose expected to take (taking into account any dose adjustments and dose omission). More specifically:

- Total dose expected to take = total dose prescribed – total dose omitted
- Total dose prescribed = sum of (prescribed dose level * corresponding dosing period)
- Total dose omitted = sum of (prescribed dose level * corresponding withheld period)

6.8. Concomitant Therapy

All medications will be coded to the generic preferred name according to the current World Health Organization (WHO) drug dictionary. All concomitant medications will be listed and

summarized using the preferred name for the safety population.

6.9. Efficacy Analyses

6.9.1. General Considerations

This section describes the statistical methods to be used for analyses intended to demonstrate the effectiveness of seliperatinib in patients with *RET* alteration solid tumors.

Disease assessments for key efficacy endpoints in this study are derived from the IRC. An Imaging Review Charter outlines the procedures governing this process. This document includes operational guidelines for the imaging schedule and parameters, data management, guidelines for the reader, and management details. Additional analyses based on investigator assessment will be provided.

The **primary analysis** of efficacy endpoints will be based on PAS, and performed separately on each tumor type subgroup as warranted by data, e.g.:

- RET fusion positive NSCLC confirmed by central lab
- RET fusion positive TC confirmed by central lab
- RET mutant MTC confirmed by central lab

Supportive efficacy analyses will be based on enrolled population, and performed on tumor type subgroups pooled across cohorts, namely:

- All NSCLC patients
- All TC patients
- All MTC patients

Additionally, supportive efficacy analyses will be performed by *cohort*:

- Cohort 1
- Cohort 2

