3.4 Investigational Plan

For this China-specific protocol, it is expected that at least 20 patients in each Cohort 1 and Cohort 2, and up to 25 patients in Cohort 3 with advanced solid tumors with evidence of a *RET* gene alteration in tumor and/or blood (e.g., gene rearrangement fusions and/or mutations, excluding synonymous, frameshift, or nonsense mutations) will be enrolled to one of three cohorts (Figure 3-1) as noted below to better characterize the safety and efficacy of selpercatinib in patients with specific abnormalities in *RET*. For Cohort 1 and 2, evidence of a *RET* gene alteration in tumor (i.e., not just blood) as defined in Table 3-1 is required (a positive germline test for a *RET* mutation is acceptable for patients with MTC).

Enrollment will be based on tumor type, type of *RET* alteration, and prior treatment:

- Cohort 1: Advanced *RET* fusion-positive solid tumor progressed on or intolerant to ≥ 1 prior standard therapy, or patients who declined or not suitable for standard first line therapy in the opinion of the Investigator (refer to Table 4-1 for standard therapies). For lung cancer, only patients harboring *RET-KIF5B*, *RET-CCDC6*, *RET-NCOA4* can be enrolled in Cohort 1. For other solid tumors, patients with any *RET* fusions can be enrolled in Cohort 1.
- Cohort 2: Advanced *RET*-mutant MTC with or without prior systematic therapy
- Cohort 3: Advanced *RET* altered solid tumor
 - Cohorts 1-2 without measurable disease;
 - Other *RET*-altered solid tumor or other *RET* alteration/activation not meeting the requirements for Cohorts 1 or 2;
 - MTC syndrome spectrum cancers (e.g. MTC, pheochromocytoma) with neuroendocrine features/differentiation or poorly differentiated thyroid cancers with other *RET* alteration/activation may be allowed with prior Sponsor approval;
 - Known cfDNA positive for a *RET* gene alteration and not able to be determined in tumor or FISH positive in tumor without PCR/NGS result may be allowed with prior Sponsor approval.

Selpercatinib will be administered in oral form at 160 mg BID. Each cycle will consist of 28 days.

Primary endpoint: ORR per RECIST 1.1 by independent review committee.

Secondary endpoint: ORR per RECIST 1.1 by investigator, DOR, CNS ORR, CNS DOR, CBR, TTR, TTBR, CBR, PFS, OS, PK, safety

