4.1 Inclusion Criteria

1. Patients with a locally advanced or metastatic solid tumor who:
 - have progressed on or are intolerant to standard therapy, or
 - no standard therapy exists, or in the opinion of the Investigator, are not candidates for or would be unlikely to tolerate or derive significant clinical benefit from standard therapy, or
 - decline standard therapy.
2. Prior MKIs with anti-RET activity are allowed. Refer to [Appendix A](#) for examples of MKIs with anti-RET activity. However, prior treatment with a selective RET inhibitor(s) (including investigational selective RET inhibitor(s), such as BLU-667, RXDX-105) is prohibited. The specific agent(s), duration of treatment, clinical benefit, and reason for discontinuation (e.g., PD, drug toxicity, or intolerance) should be documented for all kinase inhibitors the patient has been exposed to.
3. Evidence of a *RET* gene alteration in tumor and/or blood (e.g., gene rearrangement and/or mutation, excluding synonymous, frameshift, or nonsense mutations), as identified through molecular assays, as performed for clinical evaluation. The *RET* alteration result should be generated from a laboratory with certification by CNAS, EQA, CLIA, CAP or other similar certification. The Sponsor should be contacted to discuss test results from labs where such certification is not clearly demonstrated to determine eligibility.

Notes:

- A positive germline test for a *RET* mutation is acceptable for patients with MTC.
 - Local testing in a CNAS, EQA, CLIA, CAP or other similar certified laboratory is sufficient.
 - In all cases, a redacted/coded Molecular Pathology Report or other report(s) describing tumor and/or blood *RET* (and other) alternation analysis should be submitted to the Sponsor or designee during/prior to eligibility.
4. Measurable or non-measurable disease as determined by RECIST v1.1.
 5. At least 18 years of age.
 6. Eastern Cooperative Oncology Group (ECOG) performance status score of 0, 1, or 2, with no sudden deterioration 2 weeks prior to the first dose of study treatment.
 7. Life expectancy of at least 3 months.
 8. Archived tumor tissue sample available for Cohort 1 and 2.

Notes:

- Patients who do not have adequate archival tumor tissue available (refer to specific archival tissue requirements in Section 7.7.5.1) may undergo a fresh tumor biopsy, if it is considered safe to perform, prior to treatment.

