6.1. General Considerations

6.1.1. Analysis Populations

Entered population: will include all patients who signed the informed consent form

Enrolled population: will include all eligible patients.

Safety population: will include all enrolled patients who received at least one dose of selpercatinib. This population will be used for safety analysis.

Primary efficacy analysis population/primary analysis set (PAS): will include all treated patients enrolled in Cohort 1 and 2 who have *confirmed* RET fusion positive solid tumor or RET mutant MTC by central lab, respectively. The primary efficacy analysis will be conducted on this population.

Per-protocol population: will include all patients in the primary efficacy analysis population who are compliant with the study protocol without major protocol violations.

CNS response analysis population: will include all treated patients in Cohort 1 with confirmed *RET*-fusion positive solid tumor who have IRC-assessed CNS metastases at baseline.

Baseline diarrhea population: will include patients in Cohort 2 who had diarrhea at baseline. All analyses of bowel diary will be based on this population.

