6.9.2. Objective Response Rate (ORR)

6.9.2.1. Primary Analysis

ORR is a summary measure of best overall response (BOR) as defined by RECIST Version 1.1. BOR is defined as the best response designation for each patient that is recorded between the date of the first dose of seliperatinib and the date of documented disease progression per RECIST 1.1 or the date of subsequent therapy, whichever occurs first. Each patient's BOR will be categorized as complete response (CR), partial response (PR), stable disease (SD), progressive disease (PD) or not evaluable (NE).

Response (PR or CR) must be confirmed by a repeat assessment performed no less than 28 days after the criteria for response are first met. In the event that the confirmation of a CR or PR occurs at a time point following an NE assessment, the best overall response will be CR or PR. That is, the sequence of time point responses CR-NE-CR (or PR-NE-PR/CR) will be considered a best overall response of CR (or PR). When stable disease is believed to be the best response, it must also meet the minimum interval of 6 weeks (42 days) from the start of study treatment. If

the minimum time is not met when stable disease is otherwise the best time point response, the patient's best response depends on the subsequent assessments. For example, a patient who has stable disease at the first assessment, progressive disease at the second and does not meet minimum duration for stable disease, will have a best response of progressive disease. The same patient lost to follow-up after the first stable disease assessment will be considered inevaluable.

The ORR is defined as the number of patients who achieve a BOR of CR or PR that are confirmed divided by the total number of patients in the analysis population. The point estimate will be accompanied by a 2-sided 95% exact binomial CI using the Clopper-Pearson method.

The primary analysis of ORR is based on the response assessment by the IRC. The efficacy of selpercatinib will be demonstrated primarily on the primary efficacy analysis population. ORR will also be summarized by cohort (1 & 2), as well as by major tumor types across cohorts.

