6.12. Subgroup Analyses

If warranted by data, the point estimates of ORR (and 95% CI) and median DOR (and range)

based on IRC and investigator assessments will be calculated for the subgroups defined by the following:

- age (< 60 years, ≥ 60 years)
- sex (male, female)
- ECOG performance status at baseline (0, 1–2)
- smoking status (never smoked, current smoker, former smoker)
- *RET* fusion gene (KIF5B/CCDC6/NCOA4, other)
- *RET* mutation type (M918T, extracellular cysteine mutation, other)
- Prior systemic therapy use (treatment naïve vs pre-treated)
- type of prior systemic therapies (MKI including *RET*, other MKI, non-MKI)
- type of prior systemic therapies 2 (anti-PD-1/PD-L1 antibody, other)
- best overall response to most recent prior systemic therapy (CR, PR, SD, PD, NE)

Treatment naïve patients include patients who received no prior systemic therapies or who received only adjuvant/neo-adjuvant therapies; Otherwise, patients are categorized as pre-treated.

As a supportive analysis, ORR will be summarized on the **response evaluable subgroup**, defined as patients with measurable disease (at least 1 target lesion) and at least 1 post-baseline tumor assessment.

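### Pooled tumor-type ORR and CNS ORR count patients with no measurable lesion, who can respond only by CR; add a measurable-lesion ORR beside each

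*SAP*

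**What the plan says.** **Who can be enrolled.** Protocol 4.1, criterion 4, accepts "Measurable or non-measurable disease as determined by RECIST v1.1". Criterion 17 then requires at least one measurable lesion for Cohorts 1-2. Protocol 3.4 sends to Cohort 3, among others, "Cohorts 1-2 without measurable disease". Cohort 3 is capped at 25 patients and has several other entry routes.

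**Pooled ORR.** SAP 6.9.1: "Supportive efficacy analyses will be based on enrolled population, and performed on tumor type subgroups pooled across cohorts". The groups are all NSCLC, all TC and all MTC patients. SAP 6.9.2.1 confirms that "ORR will also be summarized by cohort (1 & 2), as well as by major tumor types across cohorts". The number of confirmed responders is "divided by the total number of patients in the analysis population".

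**CNS ORR.** The CNS response analysis population (SAP 6.1.1) is treated Cohort 1 patients with confirmed fusion "who have IRC-assessed CNS metastases at baseline". SAP 6.9.9 applies the ORR method to it if the data warrant.

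**Response categories.** Protocol Table 11-9 gives patients with only non-target lesions CR, Non-CR/Non-PD, NE or PD. The SAP 6.9.2.1 list of best overall responses has CR and PR and ends with "stable disease (SD), progressive disease (PD) or not evaluable (NE"). It has no Non-CR/Non-PD.

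**Existing supportive analysis.** SAP 6.12 adds an ORR in "patients with measurable disease (at least 1 target lesion) and at least 1 post-baseline tumor assessment".

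**The concern.** A patient without a target lesion stays in the denominator but can enter the numerator only through a complete response. A pooled tumor-type ORR then mixes the drug's activity with the share of patients in whom a PR cannot be recorded. The pooled figure is likely to be read beside the primary tumor-type ORR. A lower value could be taken as weaker activity outside the primary set when part of the difference comes from the denominator.

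The same holds for CNS ORR. Cohort 1's measurable lesion may lie outside the brain, so criterion 17 does not ensure a measurable CNS lesion. Protocol 7.1 requires baseline brain imaging in all fusion-positive patients, and Appendix G treats non-nodal lesions under 10 mm as non-measurable. Small, non-measurable brain metastases can therefore enter this population. CNS groups may be small, so a few such patients could move the rate a long way.

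**Working it through.** **1. The plan's own figure.** SAP Table 5.1 (protocol Table 9-1) gives a lower 95% limit of 0.41 for an observed ORR of 0.65 at n = 20. The Clopper-Pearson lower limit is the 2.5% quantile of Beta(x, n-x+1). With x = 13 and n = 20 this is 0.408, which agrees. All 42 cells of the table reproduce to within about 0.005.

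**2. Direction of the effect.** Let n be the measurable patients in a pooled group, x their responders, k the non-measurable patients and c the CR rate among those k.

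- Measurable-disease ORR = x/n
- Planned pooled ORR = (x + kc)/(n + k)

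The pooled value is lower exactly when k > 0 and c < x/n. If c = 0, the measurable-disease rate is multiplied by n/(n + k). For n = 20 that is 20/22, 20/25 or 20/30: a relative loss of 9%, 20% or 33% for k = 2, 5 or 10.

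**3. Size under assumptions.** The documents give neither k nor c. The 65% is a column of Table 5.1 and lies close to the 64% quoted in protocol 1.5 for pretreated NSCLC.

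| k | n = 20, x = 13, c = 0 (95% CI) | n = 20, x = 13, c = 10% (expected) | n = 40, x = 26, c = 0 |
|---|---|---|---|
| 0 | 65% (41-85) | 65% | 65% |
| 2 | 13/22 = 59% (36-79) | 13.2/22 = 60% | 26/42 = 62% |
| 5 | 13/25 = 52% (31-72) | 13.5/25 = 54% | 26/45 = 58% |
| 10 | 13/30 = 43% (26-63) | 14/30 = 47% | 26/50 = 52% |

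**4. CNS ORR.** With no CR in non-measurable disease, the multiplier is the share of the population that has a measurable CNS lesion. Two assumed examples with 10 patients:

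- 5 measurable, 4 responding: 4/5 = 80% (28-99) against 4/10 = 40% (12-74).
- 8 measurable, 6 responding: 6/8 = 75% (35-97) against 6/10 = 60% (26-88).

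**5. The response evaluable subgroup.** It requires a target lesion, which removes the dilution. It also removes patients with no post-baseline assessment, who cannot have a confirmed response. If u of the n measurable patients are unscanned, it reports x/(n - u) in place of x/n. With x = 13 and n = 20, u = 1 gives 13/19 = 68% and u = 2 gives 13/18 = 72%, against 65%. SAP 6.12 does not say that this analysis is run by pooled tumor type or for CNS ORR.

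**6. The missing category.** ORR counts only confirmed CR or PR, so Non-CR/Non-PD is a non-response under any label and ORR does not move. CBR (SAP 6.9.6) can move. Coded as SD lasting 16 weeks or more, such a patient counts as a benefit; coded as NE, the patient does not. If all k patients hold Non-CR/Non-PD for that long, the two codings differ by k/(n + k): 2/22 = 9, 5/25 = 20 or 10/30 = 33 percentage points for n = 20.

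**The case against.** The strongest reply is that these rates answer a different question. The SAP names its supportive population as all enrolled patients of a tumor type, and a rate over all of them is a conservative view. The protocol defines CNS ORR for patients with brain metastases, and SAP 6.1.1 follows that. This stands. The planned denominators are defensible and should stay, and lower here means lower than a measurable-disease rate.

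A reader might infer that the primary result is biased. The documents do not support that. The primary analysis set is confined to Cohorts 1-2, where criterion 17 requires a measurable lesion.

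A reader might also infer that no planned table gives a measurable-disease ORR by tumor type with unscanned patients kept in. That goes too far. The primary analysis is run by tumor type within the primary analysis set, which has no post-baseline scan condition. What is missing is the same rate with measurable Cohort 3 patients included, and a CNS version.

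Nor does the absent Non-CR/Non-PD category push ORR down (step 6). It may even be covered in part: the SAP refers to RECIST 1.1, and protocol Table 11-8 labels persistent non-target disease as incomplete response or stable disease, which points towards SD. But the time-point section of Table 11-9 keeps Non-CR/Non-PD distinct, and its best-response section has no row for it, so the coding remains open.

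The Imaging Review Charter may hold CNS reading rules, but it is not available here. Finally, Cohort 3 may contain few or no non-measurable patients of a given tumor type. If k = 0, the pooled ORR is unaffected.

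**Conclusion.** The point holds for two sets of results: the supportive pooled tumor-type ORR and the secondary CNS ORR. Each falls below its measurable-disease counterpart whenever patients without a measurable (CNS) lesion are included and their CR rate is lower than that ORR. The primary ORR and the Cohort 1 and Cohort 2 rates are unaffected by design.

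The size cannot be derived from the documents. Under the stated assumptions a 65% rate reads 59% to 43% with 2 to 10 such patients added to 20, and somewhat higher if some of them reach CR. For CNS ORR, the assumed examples fall from 75% to 60% and from 80% to 40%. The CNS reasoning assumes that RECIST 1.1 is applied to the CNS lesions in the same way as in Table 11-9.

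The response evaluable subgroup offsets this only in part and can err in the other direction. The missing response category is a separate gap that affects the best-response table and possibly CBR.

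**What to change.** 1. Keep the all-patient pooled and CNS rates as planned.
2. Add pooled tumor-type ORR among treated patients with at least one IRC-measurable lesion at baseline, and CNS ORR among patients in the CNS response population with at least one IRC-measurable CNS lesion at baseline. Count patients without a post-baseline scan as non-responders in both. Using treated patients also matches protocol 9.2, which names that population for efficacy analyses other than the primary one.
3. Drop the post-baseline-assessment condition from the response evaluable subgroup in SAP 6.12.
4. Add Non-CR/Non-PD to the best overall response categories in SAP 6.9.2.1, and state in SAP 6.9.6 how it counts in CBR.

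The cost is SAP wording and a few extra rows. No new data are needed: SAP 6.6.7 already summarizes baseline measurable lesions by IRC, and the CNS waterfall plot in SAP 6.9.9 already needs measured CNS lesions. The downside is smaller denominators and wider intervals in the added rows.
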